8.1.1.1 Data Handling Rules for ASAS40 and ASAS20

The ASAS40 and ASAS20 will be derived based on the data handling rules below. These rules will be implemented prior to performing any NRI or MI procedures, and will therefore be integrated as part of any OC summaries i.e., they are considered as OC data.

The rules will apply for all visits in AS0009 where at least one component is present at the specific visit. For summaries of maintenance of response, the ASAS responses at visits in AS0008 will not be re-derived and will be taken directly from the AS0008 database.

- If 3 components are present (and the other component is missing), and all 3 components meet the criteria for improvement, the remaining component will be assumed not to have deteriorated and the subject will be considered a responder for ASAS40 (or ASAS20).
- If at least 1 component is present (and 1 or more other components are missing) and meets the criteria for a deterioration, the subject is a non-responder for ASAS40 (or ASAS20)
- If a single component value is missing at Baseline (and the other 3 components are not missing), the percent and absolute improvement from Baseline for all visits for that component will be set to 0 for purposes of ASAS response calculations. Thus, the subject may still be considered a responder for ASAS40 (or ASAS20) if the other 3 components all meet the criteria for improvement.
 - Note that for MI any component with a missing Baseline will be excluded from the MI modelling as Baseline is included as a covariate in the model.
 - Thus, for the MI this will mean that a maximum of 3 components only will be available at each visit and all 3 components must therefore demonstrate an improvement based on the imputed values in order for the subject to be defined as a responder at that visit. In all other cases the subject will be regarded as a non-responder when the response is re-derived based on the imputed components.
- If more than 1 component value is missing at Baseline, the percent and absolute improvement from Baseline for all visits for those components will be set to 0 for purposes of ASAS response calculations. Thus, the subject would be considered a non-responder for ASAS40 (and ASAS20) at all visits.
 - Any subject with more than 1 component missing at Baseline will therefore be excluded from any summaries based on MI as there would be insufficient data available to derive a response.
- If the Baseline value for a given component is 0 the percent improvement from Baseline is not calculable. In this case the following rules will apply:
 - If the post-Baseline value is also 0, the percent and absolute improvement at that visit will be treated as 0 for purposes of ASAS response calculations.
 - If the post-Baseline value is greater than 0 and the arithmetic change from Baseline is ≥ 1.0 , then that component will be treated as having a 20% worsening and a 1-unit absolute worsening from Baseline for purposes of ASAS response calculations (i.e., the component has deteriorated).
 - If the post-Baseline value is greater than 0 and the arithmetic change from Baseline is < 1.0 , then that component will be treated as having neither improved nor worsened for purposes of ASAS response calculations.

- If the post-Baseline value is missing, it will be regarded as 0 and the percent and absolute improvement at that visit will be treated as 0 for purposes of ASAS response calculations (NB: For the MI procedure the observed data will be included in the model as received without imputation with 0, and the percent and absolute improvement will be assumed to be 0 after performing the MI, regardless of the imputed absolute values)
- For component scores with a Baseline value >0 and a post-Baseline value of 0, percentage improvement will be calculated as for any other non-missing data.

With regards to the BASFI component see [Section 8.1.3](#) for calculation in case of missing values of single questionnaire items.

With regards to the BASDAI component see [Section 8.1.4](#) for calculation in case of missing values of single questionnaire items.

Further details regarding the assumptions and assignment of worst-case imputations for NRI are provided in [Section 12.1](#).

8.1.1.2 Data Handling Rules for ASAS5/6

The ASAS5/6 will be derived based on the data handling rules below. These rules will be implemented prior to performing any NRI procedures and will therefore be integrated as part of any OC summaries.

The rules will apply for all visits in AS0009 where at least one component is present at the specific visit. For summaries of maintenance of response, the ASAS responses at visits in AS0008 will not be re-derived and will be taken directly from the AS0008 database.

- If 5 components are present (and the other component is missing), and all 5 components meet the criteria for improvement, the subject will be considered a responder for ASAS5/6.
- If all components are present and 5 components meet the criteria for improvement, the subject will be considered a responder for ASAS5/6 regardless of whether the remaining component has stayed the same or deteriorated.
- If a single component value is missing at Baseline (and the other 5 components are not missing), the percent and absolute improvement from Baseline for all visits will be treated as 0 for purposes of ASAS response calculations. Thus, the subject may still be considered a responder for ASAS5/6 if the other 5 components all meet the criteria for improvement.
- If more than 1 component value is missing at Baseline, the percent and absolute improvement from Baseline for all visits for those components will be set to 0 for purposes of ASAS response calculations. Thus, the subject would be considered a non-responder for ASAS5/6 at all visits.
- If the Baseline value for a given component is 0 the percent improvement from Baseline is not calculable. In this case the following rules will apply:
 - If the post-Baseline value is also 0, the percent and absolute improvement at that visit will be treated as 0 for purposes of ASAS response calculations.
 - If the post-Baseline value is greater than 0 and the arithmetic change from Baseline is ≥ 1.0 , then that component will be treated as having a 20% worsening and a 1-unit

absolute worsening from Baseline for purposes of ASAS response calculations (i.e., the component has deteriorated). This will not affect the ASAS5/6 response as this is based on improvement only.

- If the post-Baseline value is greater than 0 and the arithmetic change from Baseline is <1.0 , then that component will be treated as having neither improved nor worsened for purposes of ASAS response calculations. This will not affect the ASAS5/6 response as this is based on improvement only.
- If the post-Baseline value is missing, it will be regarded as 0 and the percent and absolute improvement at that visit will be treated as 0 for purposes of ASAS response calculations
- For component scores with a Baseline value >0 and a post-Baseline value of 0, percentage improvement will be calculated as for any other non-missing data

With regards to the BASFI component see [Section 8.1.3](#) for calculation in case of missing values of single questionnaire items.

With regards to the BASDAI component see [Section 8.1.4](#) for calculation in case of missing values of single questionnaire items.

Further details regarding the assumptions and assignment of worst case for NRI are provided in [Section 12.1](#).

8.1.2 Ankylosing Spondylitis Disease Activity Score – C-reactive Protein

The ASDAS-CRP consists of a number of assessments which are scored by the subject and physician and multiplied by a proven formula (van der Heijde et al, 2009) as shown below:

- $0.121 \times$ Total Back pain (BASDAI Question 2 result)
- $0.058 \times$ Duration of morning stiffness (BASDAI Question 6 result)
- $0.110 \times$ PGADA
- $0.073 \times$ Peripheral pain/swelling (BASDAI Question 3 result)
- $0.579 \times$ (natural logarithm of the (CRP [mg/L] + 1))

Back pain, PGADA, duration of morning stiffness and peripheral pain/swelling are all assessed on a numerical scale (0 to 10 units) (Lukas et al, 2009). If the CRP value is <2 mg/L, the constant value of 2mg/L should be used in the calculation. The sum of these weighted components gives the ASDAS-CRP.

If any individual components of the ASDAS-CRP are missing then the ASDAS-CRP will be regarded as missing. The imputed value for ASDAS-CRP will then be based on the imputed values for the individual components.

Disease activity categories based on ASDAS-CRP are as follows:

- ASDAS-ID: ASDAS-CRP <1.3
- ASDAS-Low Disease Activity: ASDAS-CRP ≥ 1.3 to <2.1
- ASDAS-High Disease Activity: ASDAS-CRP ≥ 2.1 to ≤ 3.5

- ASDAS-Very High Disease Activity: ASDAS-CRP >3.5

For classification of the above, MI methods will be used to impute the individual components of the ASDAS-CRP, the ASDAS-CRP will be re-derived and this will subsequently be used to derive the appropriate disease activity category.

8.1.3 Bath Ankylosing Spondylitis Functional Index

The BASFI contains 10 questions. The first 8 questions evaluate activities related to functional anatomical limitations due to the course of this inflammatory disease. The final 2 questions evaluate the subjects' ability to cope with everyday life. An NRS ranging from 0 to 10 is used to answer the questions on the test.

The arithmetic mean of the 10 scales gives the BASFI score, which is a value between 0 and 10.

In case of missing answers to 1 or 2 of the single items within the BASFI questionnaire, the BASFI score will be calculated by imputing missing items with the mean of the completed items. Then, the BASFI score will be calculated as described above. If more than 2 of the items are missing, the BASFI score will be left missing.

8.1.4 Bath Ankylosing Spondylitis Disease Activity Index

The BASDAI is the most commonly used instrument to measure the disease activity of AS. The BASDAI is a validated self-reported instrument which consists of 6 NRSs, each with 10 units to measure the severity of the 5 major symptoms: fatigue, spinal pain, peripheral joint pain and swelling, enthesitis, and morning stiffness (both severity and duration) over the last week. To give each symptom equal weighting, the average of the 2 scores relating to morning stiffness is taken. The resulting 0 to 50 sum score is divided by 5 to give a final BASDAI score between 0 and 10, with lower scores indicating lower disease activity.

The BASDAI is calculated as follows:

$$\text{BASDAI} = \frac{Q1 + Q2 + Q3 + Q4 + \left(\frac{Q5 + Q6}{2} \right)}{5} \quad (12)$$

where Q1 – Q6 are the six questions from the BASDAI questionnaire.

If 1 of the 2 morning stiffness measurements (ie, questions: [REDACTED]

[REDACTED]) is missing, the other one will be used for the morning stiffness calculation. The same imputation is also applied for the calculation of the ASAS inflammation component, which is calculated as the average of the 2 morning stiffness measurements.

If 1 major symptom of the BASDAI is missing, the sum score of the remaining symptoms will be divided by the number of symptoms assessed. If more than 1 major symptom is missing, the sum score will be set to missing.

8.1.5 Bath Ankylosing Spondylitis Metrology Index

The BASMI characterizes the spinal mobility of a subject with AS and consists of 5 clinical measures to reflect axial status: cervical rotation; tragus-to-wall distance; lateral spinal flexion; lumbar flexion (modified Schober); intermalleolar distance. Each of the 5 movements is scored according the linear BASMI definition (van der Heijde et al, 2008) (Table 8-1). The mean of the 5 scores provides the BASMI score. The BASMI score ranges from 0 to 10. The higher the BASMI score, the more severe the subject's limitation of movement due to their AS.

Table 8-1: BASMI linear definition

Clinical Movement (Unit)	S=0 If:	S Between 0 and 10:	S=10 If:
Lateral spinal flexion ^a (cm)	$A \geq 21.1$	$S = (21.1\text{cm} - A) / 2.1\text{cm}$	$A \leq 0.1$
Tragus-to-wall distance ^a (cm)	$A \leq 8$	$S = (A - 8\text{cm}) / 3\text{cm}$	$A \geq 38$
Lumbar flexion ^a (modified Schober) (cm)	$A \geq 7.4$	$S = (7.4\text{cm} - A) / 0.7\text{cm}$	$A \leq 0.4$
Intermalleolar distance (cm)	$A \geq 124.5$	$S = (124.5\text{cm} - A) / 10\text{cm}$	$A \leq 24.5$
Cervical rotation angle ^a (°)	$A \geq 89.3$	$S = (89.3^\circ - A) / 8.5^\circ$	$A \leq 4.3$

S=BASMI Score; A=assessment.

^a For cervical rotation and lateral spinal flexion, the mean of the left and right measurements will be calculated, if both are available. Otherwise, the available measurement will be used. If multiple attempted measurements are obtained, calculate the mean of the attempts. The mean of the attempts should be calculated after averaging the left and right measurements, where applicable.

For all clinical measures, values outside the ranges presented in Table 8-2 (Maksymowych, 2006) will be regarded as invalid and set to missing in the calculation of the component scores. For clinical movement parameters with repeated attempts at the same visit (ie, lateral spinal flexion, tragus-to-wall distance, cervical rotation and lumbar flexion), if only 1 attempt is considered valid per the ranges below, then this attempt will be used to calculate the BASMI score. If both attempts are considered invalid, the specific movement clinical movement parameter will be regarded as missing.

Table 8-2: BASMI linear definition permitted ranges

Clinical Movement	Range
Lateral spinal flexion (mean right/left)	0.75 to 25.00cm
Tragus-to-wall distance (mean right/left)	9.00 to 37.50cm
Lumbar flexion (modified Schober)	0.00 to 9.00cm
Intermalleolar distance	13.00 to 160.00cm
Cervical rotation (mean right/left)	0.00 to 94.00 °

For calculation of the overall BASMI score the following imputation rules will be applied:

- If 1 or 2 clinical measures for the BASMI are missing at one visit, the missing measure will be imputed by carrying the last observation forward, and the BASMI will be calculated

accordingly. This will include using AS0008 values as the last observation if applicable. In this case missing values will be carried forward from the relevant AS0008 visit until the next valid, non-missing value is present.

- If more than 2 clinical measures are missing, the BASMI score will be regarded as missing.
- Missing AS0008 Baseline values will not be imputed.

The following sequential steps will be followed when calculating the BASMI score:

- Individual assessment values (A) that are considered invalid ([Table 8-2](#)) will be discarded (ie, set to missing).
- The mean of the (valid) left and right assessment (A) values will be calculated per subject, analysis visit, parameter, and attempt (for those parameters where more than 1 attempt has been performed and there is more than 1 valid value available).
- The mean of the assessment (A) values will be calculated across attempts per subject, analysis visit and parameter (only for visits having more than 1 attempt with a valid value).
- The BASMI component score (S) will be calculated from the averaged assessment (A) values per subject, analysis visit and parameter.
- Values obtained at the ET visit and values obtained at unscheduled visits will be re-mapped as described in [Section 3.5](#). Re-mapping will be performed on a per-parameter basis prior to the calculation of the BASMI score (this method is adopted in the event that not all parameters are assessed at each visit).
- If 1 or 2 BASMI component scores (S) are missing for a given subject and analysis visit, the most recent non-missing value will be carried forward and used at the current analysis visit.
- The final BASMI score will be calculated for a given subject and analysis visit if 1 value is available for each component score (including values that have been carried forward); in this case the BASMI score is the mean of the 5 component scores (S). If 1 value is not available for each component score the BASMI score will be set to missing for that subject and analysis visit.

8.1.6 Maastricht Ankylosing Spondylitis Enthesitis Index

The MASES Index comprises 13 items (bilateral costochondral 1, costochondral 7, anterior superior iliac spine, posterior iliac spine, iliac crest and proximal insertion of the Achilles tendon sites, and the fifth lumbar vertebral body spinous process) (Heuft-Dorenbosch et al, 2003) each scored as 0 = yes or 1 = no and then summed for a possible score of 0 to 13, with higher scores indicating worse enthesitis.

If 7 or more items are available, MASES will be imputed by dividing the sum score with the number of assessments and multiplying the result with 13. If less than 7 items are available, MASES will be treated as missing.

Presence of enthesitis at Baseline should be defined as a Baseline MASES score >0.

Summaries of MASES will be restricted to subjects with a MASES >0 at AS0008 Baseline.

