10.6 MASES

Enthesitis is assessed via MASES. The MASES is an index that measures the severity (ie, intensity and extent) of enthesitis through the assessment of 13 entheses (bilateral costochondral 1, costochondral 7, anterior superior iliac spine, posterior iliac spine, iliac crest and proximal insertion of the Achilles tendon sites, and the fifth lumbar vertebral body spinous process) (Heuft-Dorenbosch et al, 2003) each scored as 0 or 1 and then summed for a possible score of 0 to 13.

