 - For MASES the MI model will be restricted to subjects with a MASES score > 0 at AS0008 Baseline. Subjects with a MASES score of zero at AS0008 Baseline will be excluded prior to performing the procedure outlined below.
- PGADA
- TNSP
- SF-36
 - For SF-36 this will be performed for the Physical Component Summary score (PCS) and Mental Component Summary score (MCS) and for each of the 8 domain scores (Physical Functioning, Role Physical, General Health, Bodily Pain, Vitality, Social Functioning, Role Emotional and Mental Health).
- ASQoL
- HADS-A and HADS-D
 - Incidence of normal HADS-A and HADS-D scores (defined as having HADS-D<8 and HADS-A<8 at the same visit) will be derived at each visit using the values for HADS-A and HADS-D obtained after MI
- CRP
 - Note that for CRP as a standalone endpoint the rules for handling measurements that are below the limit of quantification should be followed as per [Section 8.1.12](#). Thus, if any

imputed values are <0.16mg/L these will be replaced with 0.08mg/L prior to any subsequent reporting.

The missing absolute value (not the change from baseline) will be replaced by one of a set of plausible values, where each value is a Bayesian draw from the conditional distribution of the missing data given the observed data. The basic assumption in MI is that the underlying missing data mechanism is ignorable, e.g. the missing data are missing at random.

All MI procedures will be performed using data from both AS0008 and AS0009 such that missing data across both studies will be imputed. Any previous MI or last observation carried forward (LOCF) (or other e.g., next observation carried backward) imputation performed in AS0008 will not be considered for AS0009 such that the procedure will use OC data only across both studies.

As the AS0008 Week 48 time point is synonymous with the AS0009 EV time point, this will be incorporated once only into the model.

The SAS® PROC MI procedure will be used for the imputation.

The MI consists of 3 steps:

- The missing data are imputed m times to create m complete datasets.
- The m datasets are summarized.
- The results of the m summaries are combined into a single result.

The MI method will be applied as follows:

Step 1

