8.1.10 Ankylosing Spondylitis Quality of Life

The ASQoL consists of 18 items, each with a score of 0 = no or 1 = yes, so that the sum score ranges from 0 to 18, with higher scores indicating worse quality of life.

If 3 or fewer items are missing, the missing responses will be imputed with the mean of the available responses from that visit to calculate a total score. If more than 3 items are missing, the total score will be left missing.

Note that in the raw data the results are coded as 1 = yes and 2 = no; these will be re-coded as above prior to calculation of the ASQoL score.

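### SAP 8.1.6 labels MASES items 0 = yes, 1 = no, contradicting its own higher-is-worse direction; the effect on change from Baseline depends on an AS0008 coding that is not shown

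*SAP*

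**What the plan says.** SAP 8.1.6 lists 13 entheseal sites, "each scored as 0 = yes or 1 = no and then summed for a possible score of 0 to 13", and closes the same sentence with "with higher scores indicating worse enthesitis". It then states "Presence of enthesitis at Baseline should be defined as a Baseline MASES score >0" and "Summaries of MASES will be restricted to subjects with a MASES >0 at AS0008 Baseline". When at least 7 items are available, "MASES will be imputed by dividing the sum score with the number of assessments and multiplying the result with 13". SAP 4.2.1 carries the same restriction into multiple imputation: "For MASES the MI model will be restricted to subjects with a MASES score > 0 at AS0008 Baseline".

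Protocol 10.6 gives no yes/no labels. It says only "each scored as 0 or 1 and then summed for a possible score of 0 to 13", and presents the index as a measure of how severe the enthesitis is.

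Two other rules decide where the item coding applies. SAP 3.3 uses the Baseline already held in the AS0008 database without deriving it again. SAP 8.1 repeats this for derived efficacy variables and limits its own derivations to AS0009 data, a set that includes AS0008 Week 48 relabelled as the AS0009 entry visit.

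**The concern.** With yes = 0 and no = 1, an affected site adds nothing and an unaffected site adds one. The sum then falls as enthesitis worsens, which contradicts the direction stated in the same sentence, the rule that a score above 0 means enthesitis, and the protocol's description of the index.

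Impact on enthesitis is one of the other objectives, and MASES is the only listed variable that scores entheseal sites directly. A programmer who follows 8.1.6 literally would produce an AS0009 score running the wrong way. Three things use that score or the Baseline it is compared with: change from Baseline, the imputation model, and the restriction to subjects with MASES above 0.

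**Working it through.** **Assumption.** Yes means that enthesitis is present at the site. Neither MASES section shows the item question.

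**The plan's own figure.** Six bilateral sites and one midline site give 6 x 2 + 1 = 13 items. Each is 0 or 1, so the range is 0 to 13, as stated. The range is the same under either labelling. The 0 to 13 limits for imputed values in SAP Table 4-1 therefore cannot expose a reversal.

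**Score as written.** Let t be the number of affected sites among n available.

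- Intended score: (t / n) x 13.
- Score as written: ((n - t) / n) x 13 = 13 - intended score.

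The proration rule does not repair this. With 3 of 7 sites affected, the intended score is 3/7 x 13 = 5.57 and the written one is 4/7 x 13 = 7.43; they sum to 13.

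**Change from Baseline.** Let b and f be the true scores at AS0008 Baseline and at an AS0009 visit. The true change is f - b. The Baseline is imported, so there are two mutually exclusive cases.

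- Case A: AS0008 coded 0 = no, 1 = yes, and only AS0009 follows 8.1.6. Change = (13 - f) - b.
- Case B: AS0008 coded the same way as 8.1.6. Change = (13 - f) - (13 - b) = b - f.

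| True b to f | True change | Case A | Case B |
|---|---|---|---|
| 4 to 1 | -3 | 12 - 4 = +8 | 12 - 9 = +3 |
| 6 to 0 | -6 | 13 - 6 = +7 | 13 - 7 = +6 |
| 13 to 5 | -8 | 8 - 13 = -5 | removed by the filter |

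In case A the change equals 13 - b - f, which is negative whenever b + f exceeds 13. The sign is therefore not always wrong, but the value is still on a mixed scale. In case B the sign is always reversed.

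**The MASES above 0 filter.** It acts on the imported AS0008 Baseline.

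- Case A: it selects b > 0, as intended.
- Case B: it selects 13 - b > 0, that is b < 13. Subjects with no affected site (score 13) are kept, and only those with all 13 affected (score 0) are dropped.

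**Imputation.** SAP 4.2.1 fits one model to observed data from both studies, with AS0008 Baseline as a covariate. In case A the AS0008 values before the entry visit would be on the intended scale, and values from the entry visit onward on the reversed one. The documents do not allow the effect on imputed values to be sized.

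**Comparison within the SAP.** ASQoL (SAP 8.1.10) is also a yes/no sum in which higher is worse. Its items are coded the other way, "each with a score of 0 = no or 1 = yes", with a note on recoding the raw data. MASES has no such note.

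**The case against.** The best reply is that the intended direction is plain. The same section says that higher is worse and that a score above 0 means enthesitis, and the protocol agrees. This points to two swapped labels, not to a chosen reversed analysis. SAP 4.3 also planned every output except the COVID-19 ones at the Week 108 interim. SAP Amendment 2 followed review of those results, and no amendment entry mentions a MASES problem. That weighs against an unnoticed reversal in the programs, though it does not show that the programs were right. It also leaves the SAP wording uncorrected, in the only place where either document labels the item codes.

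The rank of the variable also counts. MASES is an other efficacy variable, summarised descriptively. No primary or secondary variable uses it.

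Three stronger readings are tempting, and the documents support none of them:

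- **That 8.1.6 reverses the inclusion rule.** It does not by itself, because the filter uses a Baseline that 8.1.6 never derives. The filter fails only if AS0008 was itself coded in reverse, which is not shown. Even then it does not swap the affected and unaffected groups.
- **That every improvement would be reported as worsening.** This holds in case B. In case A it fails for high scores, as 13 to 5 shows.
- **That the trial's MASES results are in fact reversed.** Neither document shows how the item data were collected or programmed.

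The reading of yes as enthesitis present is natural but inferred. SAP Amendment 1 removed the appendices that held questionnaire copies.

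**Conclusion.** The point holds as an error in the current derivation rule. Assuming that yes means enthesitis is present, the AS0009 MASES score as written is 13 minus the intended score, and nothing else in the protocol or SAP corrects it.

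The consequence is conditional on the AS0008 coding. If AS0008 was coded conventionally, the filter is sound, but change from Baseline and the pooled imputation model combine opposite scales. If AS0008 was also reversed, change from Baseline has the wrong sign and the filter admits subjects without enthesitis. These cases cannot both occur, so their effects should not be added together. The figures above are illustrations for single subjects, not estimates of the effect on the endpoint.

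Severity is low to moderate. The enthesitis objective rests on this variable, but the primary safety variables and the secondary variables are untouched.

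**What to change.** In SAP 8.1.6, relabel the items as 0 = no, 1 = yes, with yes defined as enthesitis present at the site. Add a sentence confirming that the MASES item data and scores from AS0008 and AS0009 use this same coding, and make that check before the above-0 restriction, the multiple imputation and the change from Baseline are applied.

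The cost is a line or two of SAP text and one programming check against both databases. If the programs already use the intended coding, no output changes. If they do not, the MASES derivation, imputation and summaries need to be re-run, and any MASES tables from the Week 108 interim should be checked as well.
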